6.0 Reporting

Principal Investigators (PI), Co-investigators (Co-I), and all other study staff will monitor for adverse events (AE) and protocol deviations, and staff will notify the PI immediately of any AE or protocol deviation. CIRB guidelines will be strictly adhered to. The study staff member and PI will discuss the event in its entirety: (e.g. what happened, what caused it, if it was expected or unexpected, any ways to resolve or correct the issue,etc. The PI or project manager will file a report of all SAEs and protocol deviations with the Central Institutional Review Board (CIRB), and a copy of the report is kept on file in the project binder. When participants are consented into the study, they will be notified that they may leave the study at any time without repercussions to their regular care from the VA. In the event that a Veteran is incarcerated during the study they will be formally removed from the study and study staff will immediately notify the Central IRB (CIRB) of this event.

The Principal Investigator or site PI will be responsible for contacting the CIRB within 5 working days about any serious unanticipated adverse events or unanticipated problems involving risks to participants or others and completing any reports applicable. As necessary, either the PI or Site PI will submit Form 119 (CIRB Report of Unanticipated Serious Adverse Events and Unanticipated Problems) to the CIRB, and submit a copy to the other site, thus assuring that all parts of the study are well informed about any events or problems.

They will also provide a summary report about adverse events and unanticipated problems that did not require immediate reporting to the CIRB at the continuing reviews and at study closure. The VA Central IRB table of reporting requirements time frames will be used in all cases.

Due to the pilot nature of this study and small sample size, this study will not have a Data Monitoring Committee.

7.0 Privacy and Confidentiality

Study related questionnaires will be identified with unique ID numbers for each participant and will be collected in paper format. After the written informed consent process (Aims 1 and 2) and the survey measures have been completed, the study documents will be kept in a locked file cabinet, within the locked office, within a locked building, of the study staff. Coded interview data will be manually entered by research staff into a database that will be stored on a VA server located behind the secure firewall. Windows integrated security will be used for all computer access. At the VA, all PCs, laptops, workstations, and remote devices are set to lock and are secured after being left unattended for 5 minutes or more, or by logging-off when the equipment will be unattended for an extended period. User and role permissions will be defined at the computer, file, directory server and database level to ensure data security. Source documents with private information (e.g., consent document, payment form, etc.) will be stored in a locked file cabinet, within the locked office, within a locked building, of the research staff. Research records may be released or disclosed if required by federal law. Study participants will not be specifically identified in any publication of research results. Records will be kept according to current VA regulations.

All local policies will be adhered to for information security purposes. All identified data will be behind the VA Firewall, and only current VA study staff will have access to this data on an as needed basis. Research staff who leave the study will be removed from the study staff via the Study Staff Form and their access to the study drives and/or documents will also be terminated. If there is an improper use or disclosure of study data, we will notify the ISO and Privacy Officer immediately of said occurrence.

All research records will be maintained in accordance with the Veterans Health Administration (VHA) Records Control Schedule. Paper records will be disposed of using methods deemed appropriate by the VAPHS Privacy Officer, and all electronic data will be sanitized using methods rendered appropriate by the VAPHS ISO.

7.1 Communication Plan

The Principal Investigator ultimately will be responsible for monitoring the data and safety with involvement from all of the study investigators. They will ensure that all relevant CIRB policies, procedures and stipulations are being followed. They also will be responsible for ensuring that other investigators and project staff adhere to the VA CIRB policies including: (1) all participants will understand, agree to and sign a written consent form before participating; (2) strict adherence to a participant's right to withdraw or refuse to answer questions will be maintained; (3) the assessments will be

completely confidential and no names will be associated with the assessment data; (4) consent forms and identifying information will be kept separate from the actual participant data; (5) all identifying information (consents, tracking data) will be kept locked at all times and computer files will be saved with passwords; (6) participants will be informed in writing in the consent form how to contact the PI, the study coordinator, and VA CIRB office with any questions and/or concerns.

The PI will directly supervise the data manager and the project coordinator and will be responsible for monitoring confidentiality procedures. Quality control and reliability of screening, baseline and follow-up assessments will be monitored by [name] throughout the trial via regular meetings and observation of the project coordinator conducting standardized assessments.

## Statistical Analysis Plan

Grant Title: Peer Based Suicide Prevention

ClinicalTrials.gov ID: NCT04222673

Sponsor: VA Office of Research and Development

Document date: March 8, 2022

Given the small sample size and recommendations for pilot studies, quantitative analyses were descriptive (e.g., frequencies, means) and based on the Reliable Change Index (RCI) for each participant for each outcome measure. The RCI is used to determine whether pre- to post-score differences are statistically reliable and to categorize changes as either improved, deteriorated, or indeterminate. A statistical threshold of RCI score  $z = \pm 1.96$  and  $p < .05$  was used to establish clinical significance.

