The PREVAIL model uses a 4-step process as a guide to their interactions with patients each of the weekly meetings: (1) Invite discussion about hope- and belongingness-related topic; (2) Learn to find out more about what participants have already tried and what participants think might be helpful or relevant to their situation; (3) Share suggestions based on their personal experience or knowledge; and (4) Motivate "change talk," including how taking action might be helpful, how they might practically go about implementing changes, and whether they have made a commitment to change. The PREVAIL model also includes having PSs "check in" midway through the 3-month intervention to gauge the patient's preference for more- or less-structured conversations or sharing, and to remind participants they are half-way through the intervention so they anticipate and prepare for termination at the 3-month point.

The second phase will involve pilot testing the feasibility and acceptability of the adapted PREVAIL, rehabilitative measures, and suicide-related outcomes for use in a rigorous prospective study. To mirror recommendations for adapting interventions and pilot studies to help prepare for larger trials,^{7,28} we will recruit 12 high suicide risk Veterans who will participate in a 3-month "pre-pilot" and provide feedback on how the

intervention may be improved. Pre-testing adapted materials and using retrospective feedback from participants are recommended steps to identifying any further changes prior to further implementation.^{7,8} After making any necessary modifications, for the third phase or 3-month “formal pilot”, we will recruit a second group of 12 Veterans who are at high suicide risk to further evaluate the feasibility and acceptability of recruitment, retention, and assessment procedures to be used in a future randomized trial. We will draw upon the support and existing resources at the VA Connecticut campuses, which house on the largest PSs programs.

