Veterans in both the pre-pilot and formal pilot will each meet with research staff for a Baseline Visit, Post-Intervention Visit, and a 3-Month Follow-Up Visit. All participants will also be invited to participate in an in-depth qualitative interview shortly after their 3- month follow-up assessments to assess their views of the intervention, including barriers, strengths, and recommended changes. All qualitative interviews will be recorded and transcribed. During the interviews, participants will be encouraged to avoid using names. If any name is recorded, it will be omitted from the written transcript (i.e., the transcript may read [name] in place of the actual name). Only the study team will have access to data collected by questionnaires, interviews, and medical record data.

Risks and Risk Minimization

Needs Assessment (Aim 1): There are no foreseeable physical or medical risks in this portion of the project. However, potential participants will be informed of the general nature of the study, what their involvement entails, the risks/benefits, and limitations to confidentiality prior to providing informed consent. The site PI for VA Connecticut and Co-I will contact key staff and make arrangements for interviews. Three Veterans will be identified pursuant to a HIPAA waiver, and a letter will be mailed to them inviting their participation.

We will minimize risks to interview participants by thoroughly explaining to them that participation in the project is strictly voluntary and that the decision not to participate will have no bearing on their employment. Individual names of employment settings and associated responses will not be provided to any other agency. In reports, publications, or presentations using project research data, we will report the data in aggregate form and/or change names and disguise the identity of any individual we describe or quote for purposes of illustration or example.

Pre-and Formal Pilot Testing (Aim 2): A potential risk to study participants is clinical deterioration of their mental health and/or an increase in suicidal thoughts or behaviors

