5.6 Data Analysis

Per SPiRE protocol and discussions with an RR&D Scientific Program Manager, calculations for power and estimated effect size are not required because our proposal involves piloting a rehabilitation intervention with a small, high risk sample of VHA patients (as opposed to determining effectiveness in large samples via inferential statistical hypothesis testing).

Aim 1

Qualitative analyses of interviews from the needs assessment will be conducted with empirical phenomenological procedures used successfully by our team in previous studies.⁵⁷ Verbatim transcripts of audio recordings from the interviews will be distributed to the Co-Investigators. Each researcher will independently review, analyze, and code the transcripts for themes that characterize participants' experiences. After creating a narrative summary using the participants' own language, they will review each of their summaries to compare/contrast the identified themes before coming to consensus about important themes. A synthesized report will summarize the overarching themes.

Aim 2

WOC employees from the Program for Recovery and Community Health (PRCH) will conduct the data analysis for this aim. In line with SPIRE guidelines and recommendations for pilot studies,^{28,89} our focus will be on the feasibility of the intervention and assessment of outcomes. Therefore, quantitative analysis will be mostly descriptive in nature (e.g., frequencies, percentages, means, standard deviations) and will focus on the estimation of confidence intervals. This includes descriptive statistics on each of the measures at each assessment period, creation of confidence-intervals, and visual plotting of data to observe potential trends in the data associated with the intervention. Formal hypothesis testing will not be conducted as comparisons of outcomes would be unreliable estimates of any true effect given the small sample size. Instead, analyses will be used to evaluate the feasibility of measuring the primary outcomes and potential mediators as well as to inform decisions about power and sample sizes in a larger trial. Qualitative analyses of post-intervention interviews with Veterans will follow the same procedures as described for Aim #1. Qualitative analysis of interviews and/or focus groups with Peers Specialists conducted after completing the PREVAIL training and the pre-pilot of the intervention will also follow the same procedures as described in Aim #1.

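### The SAP labels statistically reliable change as clinical significance and is not reconciled with protocol 5.6; neither text ties its analysis to the progression thresholds

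*SAP*

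**What the plan says.** **SAP.** The SAP is one paragraph, dated March 8, 2022, and written in the past tense. It says that "quantitative analyses were descriptive (e.g., frequencies, means) and based on the Reliable Change Index (RCI"), computed for each participant on each outcome measure. The index is said to determine "whether pre- to post-score differences are statistically reliable and to categorize changes as either improved, deteriorated, or indeterminate". The next sentence says that a threshold of z = ±1.96 with p < .05 "was used to establish clinical significance".

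**Protocol 5.6, Aim 2 (Version 5.0, same date).** The quantitative analysis is mostly descriptive ("e.g., frequencies, percentages, means, standard deviations) and will focus on the estimation of confidence intervals"). It goes on: "This includes descriptive statistics on each of the measures at each assessment period, creation of confidence-intervals", and plots. One stated purpose is "to inform decisions about power and sample sizes in a larger trial". The section does not mention the RCI.

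**Assessment times.** Protocol 5.1 has Veterans in both pilots meet research staff "for a Baseline Visit, Post-Intervention Visit, and a 3-Month Follow-Up Visit".

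**Feasibility.** The Abstract makes progress to a randomized trial depend on more than 50% of eligible participants enrolling and more than 70% of enrollees completing follow-up. Protocol 5.1 uses the second group of 12 "to further evaluate the feasibility and acceptability of recruitment, retention, and assessment procedures to be used in a future randomized trial". Protocol 5.2 plans 12 + 12 participants and assumes 75% retention, which leaves 18 with outcome data.

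**The concern.** There are three linked issues.

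1. **The label.** The SAP describes the RCI correctly as a test of statistical reliability, then treats the same cut-off as proof of clinical significance. A report that follows this wording would describe change beyond measurement error as clinically significant improvement. In a single-arm pilot of Veterans at high suicide risk, readers could take that as evidence of benefit.

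2. **Two unreconciled texts.** Someone working from the SAP alone could produce RCI counts and a few means and consider the plan fulfilled. Counts of improved, deteriorated and indeterminate participants give neither an SD nor an interval, so they cannot do the sizing job that 5.6 sets. The 3-month follow-up could also go unsummarised.

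3. **The go/no-go criteria.** The decision that the pilot exists to support rests on two percentages. Neither analysis text mentions their thresholds, and neither document says which group of participants they apply to.

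**Working it through.** **Step 1: the plan's own figures.** Protocol 5.2: 24 × 0.75 = 18, which reproduces. SAP: the two-sided p at z = 1.96 is 0.0500, which agrees with p < .05. No stated figure is wrong.

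**Step 2: what ±1.96 measures.** RCI = (post − pre) / [SD × √(2(1 − r))], where SD is the baseline SD and r the scale's reliability. Setting |RCI| = 1.96, the change needed in baseline SDs is 1.96 × √(2(1 − r)). The documents give no r, so these values are assumptions:

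| Assumed r | Calculation | Change needed (baseline SDs) |
|---|---|---|
| 0.70 | 1.96 × √0.60 | 1.52 |
| 0.80 | 1.96 × √0.40 | 1.24 |
| 0.90 | 1.96 × √0.20 | 0.88 |
| 0.95 | 1.96 × √0.10 | 0.62 |

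A change of 1.0 SD would be called clinically significant on a scale with r = 0.90 and indeterminate on one with r = 0.80. Only reliability enters; nothing clinical does.

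**Step 3: the two analysis texts side by side.**

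| Item | Protocol 5.6 | SAP |
|---|---|---|
| Confidence intervals | Stated focus | Not named |
| SDs | Named | Not named |
| Time points | Each assessment period (three, from 5.1) | Pre to post for the RCI; none given for the descriptives |
| RCI | Not named | Basis of the analysis, with descriptives |
| Link to the other text | None | None |
| Abstract thresholds | Not mentioned | Not mentioned |

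The 3-month summary is not spelled out in 5.6. It follows from reading that section's reference to every assessment period together with 5.1.

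**Step 4: why the cohort needs stating.** More than 70% of 24 means more than 16.8, so at least 17. More than 70% of 12 means more than 8.4, so at least 9. Suppose 9 of 12 complete in the pre-pilot and 8 of 12 in the formal pilot. All 24 give 17/24 = 70.8%, which meets the criterion. The formal pilot gives 8/12 = 66.7%, which does not.

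**Step 5: precision, for context.** Exact (Clopper-Pearson) limits are the 0.025 quantile of Beta(x, n − x + 1) and the 0.975 quantile of Beta(x + 1, n − x).

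- Retention: 18/24 = 75%, CI 53.3% to 90.2%; 9/12 = 75%, CI 42.8% to 94.5%.
- Enrolment: the number of eligible Veterans is not given. If 24 enrol from an assumed 30, 40 or 47, the rate is 80% (61% to 92%), 60% (43% to 75%) or 51% (36% to 66%).
- Mean change: the 95% half-width is t(0.975, n − 1)/√n, in units of the SD of change. It is 0.50 at n = 18 and 0.77 at n = 9 (75% of 12).
- SD at n = 18, normal data assumed: the 95% limits are √(17/χ²) times the estimate, using the 0.975 and 0.025 quantiles of χ² on 17 df, or 0.75 to 1.50. Sample size goes with SD², so the next trial's N for a fixed difference could range from 0.56 to 2.25 times the value planned.

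These widths would be the same under any wording of the SAP. They show what the intervals in 5.6 would tell the planners of the next trial.

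**The case against.** **It is an omission, not a conflict.** The SAP gives its descriptives as examples, so it excludes nothing, and its pre-to-post wording describes only the RCI. It does not withdraw 5.6, and one report can satisfy both texts. This stands. A reader might infer that the SAP contradicts or replaces 5.6, but the documents do not support that.

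**Feasibility is covered.** Protocol 5.6 says its focus is feasibility and provides for percentages and confidence intervals. Protocol 5.2 names the rates, and the Abstract gives each threshold a denominator. This also stands. A reader might infer that the progression criteria have no analysis at all, which goes too far. Only the explicit link to the thresholds and the choice of cohort are missing.

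**The wide intervals come from n.** This is correct. A reader might infer that 75% retention fails the 70% criterion because the interval includes 70%. The Abstract states a point rule, and 75% meets it. The widths are no error in the SAP, and 5.6 itself acknowledges that the sample is too small for reliable comparisons of outcomes.

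**The label is one phrase, and the reliabilities may be in the cited sources.** The sources cited in the SAP cannot be checked here, so its lack of stated values is not counted as an error. But the phrase governs how every RCI result is described, and the SAP's own preceding sentence shows that it is wrong.

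**Conclusion.** The label is wrong as written. On the SAP's own account, the RCI shows whether change is statistically reliable, and no clinical benchmark accompanies the cut-off. The illustration of 0.88 against 1.24 baseline SDs rests on assumed reliabilities of 0.90 and 0.80. The conclusion does not, because the cut-off in SD units depends on reliability alone whatever its value.

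The difference between the SAP and 5.6 is an unreconciled omission. It matters because intervals are the stated focus of 5.6 and the next trial's size depends partly on them. The gap on progression criteria is narrower: a missing link to the Abstract's thresholds and an unstated cohort, which Step 4 shows can decide whether the retention criterion is met.

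The design and the planned numbers are not in question. These corrections should be made because they affect how the pilot is interpreted and how the next trial is planned.

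**What to change.** 1. **RCI.** Call the categories reliable change (improved, deteriorated, indeterminate) and drop the claim of clinical significance. State the reliability coefficient and SD used for each scale, with their source. Present the counts as a supplementary display.
2. **Outcomes.** Carry 5.6 into the SAP or the report. For each measure give the mean and SD at each assessment, and the mean change from baseline with its SD and 95% CI at post-intervention and at 3 months.
3. **Progression.** Report enrolment and follow-up completion, with numerators, denominators and exact 95% CIs, beside the > 50% and > 70% thresholds. Do this for all 24 and for the formal pilot of 12, and say which cohort the decision uses. Keep the point rule; no lower-limit rule is proposed.

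The SAP's past tense suggests that the analysis may be complete. If so, make the same corrections in the report, and if the deciding cohort is chosen after the data were seen, say so.

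The cost is a few sentences and routine tables. The outcome data are already collected under the protocol; the enrolment rate also needs a count of eligible Veterans. The intervals will be wide, which is a fair picture of what 24 participants can show.

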5.2 Recruitment Methods

Recruitment-Aim 1

We will recruit a diverse group of 12 individuals for the Needs Assessment phase of the project to inform the adaptation of PREVAIL. This group will be comprised of Veterans (3), Peer Specialists (3), Providers from behavioral health, inpatient and outpatient psychiatry, and other relevant departments (4), and Clinical Directors (2).

We will obtain a waiver of HIPAA authorization to identify Veterans to participate in the Needs Assessment. Once these Veterans are identified, they will be mailed a letter informing them about and requesting their participation in the Needs Assessment interviews. A member of the study team will follow-up with a telephone call approximately one week after the letter is sent. The team members will attempt to reach the Veterans by phone 3 times and will leave no more than two messages. Providers, clinical directors, and Peer Specialists will either be sent an email or will be verbally invited in person to participate in the Needs Assessment.

Recruitment for the Steering Committee

The Steering Committee will be comprised of researchers and VHA leadership. The site PI will identify appropriate VA staff and other providers and will contact them by phone or email.

Recruitment-Aim 2

We will recruit 4-6 Peer Specialists who are currently working in VA Connecticut Healthcare System (VACT) to receive training in the PREVAIL model and to deliver the intervention for the pre- and formal pilot. All of the selected Peer Specialists have been trained and certified, with multiple years of clinical experience working with Veterans in recovery, including those who have been at some point 'flagged' for suicide risk.

We will include a sample of up to 24 VHA patients identified as being high-risk for suicide at the VA Connecticut Healthcare System (VACT) to receive the pilot intervention as an adjunct to usual care. Patients will be considered high suicide risk if they have a Patient Record Flag (PRF) in their medical chart for a recent suicide attempt, serious suicidal ideation, or other warning signs of acute suicide risk. The VACT Suicide Prevention Coordinator maintains a list of patients with active PRFs. This population is targeted because they are at greatest risk for suicide and therefore most in need of intervention.

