In addition to reaching out to Veterans on the high-risk list, we also will engage Veterans via the New Haven VA psychiatric Emergency Room, inpatient units, and individual New Haven clinicians. Specifically, we will engage with staff to find out if any Veteran has received a score on the Columbia-Suicide Severity Rating Scale Screen of 3 or greater in the last three months. This measure is used commonly in the VA. Such a score is known to be an optimal cut off score for identifying individuals who would likely attempt suicide. In a recent study of nearly 19000 patients, those scoring over the cut-off of ≥ 3 had almost four times the odds of dying by suicide within 1 week and 1 month, respectively, and doubled the odds of dying within a year⁹⁰. We will also engage with individual clinicians to assess whether any of their patients have recently received a score of ≥ 3 on the Columbia measures. In addition, we will ask these staff about any Veteran who made a suicide attempt in the last three months. Thus, the additional recruitment criteria we are adding will be:

- Any Veteran from the New Haven VA psychiatric Emergency Room, the New Haven inpatient units, or from individual New Haven clinicians who received a score on the Columbia-Suicide Severity Rating Scale Screen of 3 or greater in the last three months
- Any Veteran from the New Haven VA psychiatric Emergency Room, the New Haven inpatient units, or from individual New Haven clinicians who made a suicide attempt within the last three months

Each month, there are approximately 105 VHA patients with PRFs for suicide risk at the CT VA campuses. In addition to those Veterans with a PRF, we also will be recruiting those Veterans with suicidal ideation or attempts. This pool of Veterans should be sufficient to recruit participants for the pre-pilot (n=12) and formal pilot (n=12). Assuming a 75% retention rate (as achieved in [name] PREVAIL pilot)¹⁵ this will yield a final sample of 18 patients with outcome data at post-intervention and 3-month follow-up. This sample size will yield reasonably precise estimates of feasibility in terms of actual rates of recruitment, retention, compliance/fidelity to intervention, and completion of outcome assessments.

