5.5 Study Evaluations

Measures

The measures used to collect data for Aims 1 and 2 include data from the CPRS record as well as several rehabilitation and depression & suicide variables described in further detail below. Additionally, a study-specific form will be used to collect information about age, sex, race, ethnicity, employment, education, income, and marital status.

Rehabilitation Variables

Sheehan Disability Scale (SDS)⁶⁴. The SDS uses 3 items to measure how much work, social life, and family life are impaired by mental health symptoms. The SDS has been widely used in diverse samples,⁶⁵⁻⁶⁷ including Veterans,^{68,69} and found to be psychometrically sound and sensitive to treatment effects.

Temple University Community Participation scale (TUCP)⁷¹. The TUCP is a 26-item measure of community inclusion in the past month. The TUCP has been used in previous studies with good reliability.⁷¹⁻⁷⁴

Questionnaire about the Process of Recovery (QPR)⁷⁵. The QPR contains 15 items that measure connectedness, hope, identity, meaning, and empowerment. The QPR has demonstrated high internal and convergent validity as well as sensitivity to change.^{76,77}

Quality of Life Enjoyment and Satisfaction Questionnaire (Q-LES-Q-SF). The Q-LES-Q-SF consists of 16 items to assess life satisfaction in the past week. The Q-LES-Q-SF has been used extensively with Veterans as part of the National Health and Resilience in Veterans Study (NHRVS).

Depression and Suicide Variables

Quick Inventory of Depressive Symptoms (QIDS)⁷⁹. The QIDS consists of 16 questions to assess depression severity. The QIDS has demonstrated high reliability, validity, and sensitivity to treatment change,⁸⁰, including among Veterans.⁸¹

Columbia-Suicide Severity Rating Scale (C-SSRS)⁸². The C-SSRS is used to assess suicidal ideation (past 30 days) and behaviors (past 3 months). Suicide ideation items include: (1) wish to be dead, (2) non-specific suicidal thoughts, (3) suicidal thoughts with methods, (4) suicidal intent, and (5) suicidal intent with plan. The suicide behavior subscales include: (1) attempts (actual, aborted, interrupted), (2) preparatory behavior, and (3) non-suicidal self-injurious behavior. We will also use two measures of psychosocial variables that potentially mediate suicide risk and are hypothesized to be impacted by PSs.

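### The SAP's pre-to-post RCI exempts no outcome measure, so for the C-SSRS it can class a repeat suicide attempt as indeterminate and cannot register worsening from the top ideation level

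*SAP*

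**What the plan says.** The SAP's single analysis paragraph calls the quantitative work descriptive and bases it on the RCI "for each participant for each outcome measure". The index is there to determine "whether pre- to post-score differences are statistically reliable and to categorize changes as either improved, deteriorated, or indeterminate", and a threshold of z = ±1.96 with p < .05 "was used to establish clinical significance". The SAP does not list the measures covered and exempts none. It gives no RCI formula, SD or reliability.

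Protocol section 5.5 includes the C-SSRS among the depression and suicide variables, with a 30-day window for ideation and a 3-month window for behaviors. It lists five ordered ideation items, the upper ones being "3) suicidal thoughts with methods, (4) suicidal intent, and (5) suicidal intent with plan". It does not say how ideation is scored, or whether behaviors are recorded as yes/no or as counts.

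Section 5.2 gives several ways to qualify as high risk. One is a "Patient Record Flag (PRF) in their medical chart for a recent suicide attempt, serious suicidal ideation, or other warning signs of acute suicide risk". Two were added for Veterans from the psychiatric emergency room, inpatient units or individual clinicians: a "score on the Columbia-Suicide Severity Rating Scale Screen of 3 or greater in the last three months", or being a Veteran "who made a suicide attempt within the last three months". Section 5.1 sets the intervention at 3 months.

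**The concern.** An RCI asks whether the difference between two scores exceeds measurement error. That suits a multi-item scale with room to move both ways. It suits an event such as a suicide attempt poorly, because the event matters in itself whether or not it also happened before. It also suits a short, bounded severity level poorly when people are enrolled near the top.

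Aim 2 asks, among other things, whether the suicide outcomes are usable in a later controlled trial. The SAP makes the RCI its test of clinical significance. A C-SSRS table built by this rule could show nobody deteriorated although a Veteran attempted suicide again during the intervention, or moved from intent to intent with a plan. Read alone, it would be a poor guide to how the C-SSRS should be used next.

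**Working it through.** **The plan's own figures.** The two-sided p-value at z = 1.96 is 0.0500, which agrees with the SAP's threshold. The protocol's expected sample with outcome data is 24 × 0.75 = 18, as stated in section 5.2.

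**Formula (assumed, since the SAP prints none).** RCI = (post − pre) / [SD × √(2(1 − r))], with higher scores worse and r the reliability. The smallest change that counts must exceed 1.96 × SD × √(2(1 − r)). The documents give neither SD nor r for the C-SSRS, so both are varied.

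**Windows.** The baseline behavior window covers the 3 months before the baseline visit. The post window covers the 3 months before the post visit, which is roughly the intervention period. An attempt that qualified a Veteran can therefore lie in the baseline window and a repeat attempt in the post window.

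**Attempt in both windows.** With yes/no scoring or equal counts (1 then 1), RCI = 0 / [SD × √(2(1 − r))] = 0. The class is indeterminate for every SD and r.

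**Other attempt patterns.**
- No attempt, then an attempt (yes/no): the SD is √(p(1 − p)) for baseline prevalence p. Over p = 0.1–0.9 and r = 0.5–0.9 the RCI runs from 2.00 to 7.45, so the class is deteriorated in every case tested.
- Counts, 1 then 2, over r = 0.5–0.9: RCI 2.00–4.47 at SD 0.5 (deteriorated); 1.00–2.24 at SD 1.0 (deteriorated only at high r); 0.67–1.49 at SD 1.5 (indeterminate). A rise from 0 to 1 is the same one-unit change, so under count scoring it gives the same values.
- Counts, 2 then 1: the same values with a minus sign. At SD 0.5 that is −2.00 to −4.47, so the class is improved despite a new attempt.

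**Ideation, assuming a 0–5 score.** Change needed, in points:

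| SD | r = .5 | r = .6 | r = .7 | r = .8 | r = .9 |
|---|---|---|---|---|---|
| 1.0 | 1.96 | 1.75 | 1.52 | 1.24 | 0.88 |
| 1.25 | 2.45 | 2.19 | 1.90 | 1.55 | 1.10 |
| 1.5 | 2.94 | 2.63 | 2.28 | 1.86 | 1.31 |
| 2.0 | 3.92 | 3.51 | 3.04 | 2.48 | 1.75 |

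- From level 5 no rise is possible, so deteriorated is unreachable.
- From 4 to 5 (1 point), r must be at least 1 − 1/(2 × 1.96² × SD²) = 1 − 0.1302/SD². That is .870 at SD 1.0, .942 at SD 1.5 and .967 at SD 2.0.
- From 3 to 5 (2 points), r must be at least 1 − 0.5206/SD². That is .479 at SD 1.0, .769 at SD 1.5 and .870 at SD 2.0. The move is classed as deteriorated throughout the SD 1.0 row, but not at SD 1.5 with r = .7, where 2.28 points are needed.

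**Which SDs are plausible.** If the SD comes from this sample and all 18 baselines lie at 3–5, its largest value (half at 3, half at 5) is √(18/17) = 1.03. A larger sample SD implies some Veterans start below 3, and they have more room to worsen.

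**The case against.** The best defence has four parts.

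First, the SAP never names the C-SSRS, and the protocol never says how it is scored. Yes/no, count and 0–5 scoring are all the reader's assumptions. That is correct. Even so, the SAP's scope is every outcome measure, and both natural scorings of an attempt give zero change for an equal repeat.

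Second, the attempt result concerns a subset. A reader might infer that any attempt during the intervention goes unclassed. The documents do not support that. The problem needs an attempt inside the baseline window, whereas a flag may rest on ideation or other warning signs, and a qualifying attempt may have dropped out of the window by the baseline visit. Section 5.4 still lists the flag alone as the high-risk criterion. A first attempt scored yes/no was classed as deteriorated in every case tested.

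Third, a reader might infer that worsening ideation has almost no room to be detected. That also goes too far. At SD about 1.0, which is close to the most that baselines confined to 3–5 allow, a move from 3 to 5 is classed as deteriorated. The screen cut-off of 3 is one entry route among several and looks back three months, while baseline ideation covers 30 days. Lower baselines are therefore possible.

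Fourth, attempts are not lost. Protocol section 5.6 plans descriptive summaries of every measure at every visit, the Abstract plans a chart review of visits for suicidal behavior, and section 6.0 covers adverse events. The progression criteria in the Abstract (enrollment above 50%, follow-up completion above 70%) do not use the RCI. All of this stands, and it confines the point to the RCI table. It does not make that table correct for the C-SSRS.

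**Conclusion.** The concern holds in a limited form: the stated rule covers the C-SSRS and misclassifies some of what that instrument records.

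Two results do not depend on SD or reliability. An attempt in both windows with an equal score is indeterminate, and a Veteran at ideation level 5 cannot be classed as deteriorated. The first rests on yes/no or equal-count scoring, the second on a 0–5 score. The rest is conditional: a move from 4 to 5 needs r of about .87 or more at SD 1.0 and .94 or more at SD 1.5, and a move from 3 to 5 is missed only at larger SDs with lower reliability. A fall from 2 attempts to 1 is classed as improved when the SD is small or reliability is high.

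How many Veterans this affects cannot be estimated, because the documents give no share entering with an attempt inside the baseline window. The fault is one of classification and reporting. It does not show lost safety data or a distorted decision to proceed. It is worth correcting because a better display is available from data already planned.

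**What to change.** In the SAP, keep the RCI for the multi-item scales, name the measures it applies to, and exempt the C-SSRS. Then report:

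- **C-SSRS behaviors as events:** the number of Veterans with any attempt or preparatory behavior in the window before the post visit, and in the window before the 3-month follow-up, each cross-tabulated with behavior at baseline.
- **C-SSRS ideation as a level table:** baseline level by post level, with the number newly at level 4 or 5.

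The cost is a few lines of SAP text and small tables from assessments already scheduled, with no new visits or instruments. The C-SSRS would lose the three-category format shared with the other measures, and with about 18 Veterans many cells would be small.
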